12.4.1 Unanticipated Adverse Device Effects Reporting

A UADE is "any serious adverse effect on health or safety or any life-threatening problem or death caused by, or associated with, a device, if that effect, problem, or death was not previously identified in nature, severity, or degree of incidence in the investigational plan or application (including a supplementary plan or application), or any other unanticipated serious problem associated with a device that relates to the rights, safety, or welfare of subjects" (21 CFR 812.3[s]).

Investigators should report UADEs to the sponsor and to the IRB as follows: Investigators are required to submit a report of a UADE to the sponsor and the reviewing IRB as soon as possible, but in no event later than 10 working days after the investigator first learns of the event (21 CFR812.150[a][1]).

Sponsors must immediately conduct an evaluation of a UADE and must report the results of the evaluation to FDA, all reviewing IRBs, and participating investigators within 10 working days after the sponsor first receives notice of the effect (21 CFR 812.46[b], 21 CFR 812.150[b][1]).

Clinical investigation stopping rules in case of vascular occlusion:

Special care will be taken in case of vascular occlusion which is a rare, but serious, adverse event; this encompasses vascular embolic events which may lead to skin necrosis, vision loss or stroke.

In the event that such a complication occurs, the enrollment and treatment at the investigational site will be suspended and a root cause investigation has to be conducted to determine the cause of the event. If the investigator didn't properly follow the treatment procedure, he/she will be re-trained before being allowed to recruit further subjects.

In case this event was unanticipated and the investigator did follow the treatment procedure correctly, the entire clinical investigation has to be immediately suspended and no subjects

15 Mar 2021

should be enrolled until the event can be properly characterized and an appropriate treatment strategy to avoid this unanticipated event can be devised.

For received reports containing any event relating to incidences of visual distributions, in the form of a site query ('Device Safety Query for Additional Information' form, see SMP 9.5.4), the following information must be urgently requested:

- Depth of injection (i.e. subcutaneous or supraperiosteal)
- The injection volume
- The symptoms that were observed
- The time to event onset, and resolution
- Any interventions that were implemented
- The symptoms that were observed
- The time to event onset, and resolution
- Any interventions that were implemented

If a response to the aforementioned queries is not received within 24 hours, a follow up reminder will be sent, and the queries escalated to the Clinical Monitor and Project Manager.

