6.1 Potential Risks

In general HA fillers are the most frequently used dermal fillers and are considered the most predictable, having been shown to be safe and well-tolerated, with studies reporting mild adverse events which resolve quickly. Risks associated with the clinical investigation IMDs may include common, short-term events like discomfort, redness, swelling or bruising (DeLorenzi, 2013).

Less likely and uncommon events may include short-term events like injection site necrosis or hypersensitivity or medium-term events like visibility of injectant (blanched, bluish or white papule or lumps) or nodule formation (DeLorenzi, 2013; Funt & Pavicic, 2013; Ibrahim, Overman, Arndt, & Dover, 2017).

Rare but serious adverse events associated with the unintended intravascular injection of dermal fillers in the face have been reported and include temporary or permanent vision impairment, blindness, cerebral ischemia or cerebral hemorrhage, which are leading to stroke, skin necrosis, and damage to underlying facial structures (Beleznay et al., 2015). Possibly unrelated events like headache, sinusitis, respiratory symptoms, itching, acne and herpes simplex reactivation have been occasionally reported after treatment with dermal fillers (Bugge et al., 2007; DeLorenzi, 2013; Funt & Pavicic, 2013; Gazzola, Pasini, & Cavallini, 2012; Requena et al., 2011).

The risks will be mitigated by following strategies:

- engagement of investigators who are experienced in use of dermal fillers for correction of NLFs to ensure correct application of the investigational device
- regular follow-up assessments throughout the study duration, which will allow for timely recognition and management of potential AEs
- evaluation of vision changes through visual examinations before and after treatment
- protocols at each investigational site for immediate intervention in the event of unintended vascular injection
- phone calls for safety follow-up: the subjects will be contacted by phone three days after initial, touch-up and repeat-treatments to check their health condition, and will be

CPH-301-201200F

also instructed to immediately contact the treating investigator in case of any health concern occurring between the scheduled visits.

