10.8.4 Abnormal Visual Examinations

The following results from visual examinations at Baseline will be considered abnormal and will exclude the subject from participation in the study:

- Snellen acuity test: any result worse than 20/40 (with corrections, if applicable)
- Confrontational visual field test: abnormal is defined as the inability of the subject to correctly identify/count the examiner's fingers in one or more quadrants in one or both eyes.

Ocular motility: abnormal is defined as the inability of the subject to follow the
finger of the tester smoothly; inability to focus on the finger as it points to the nose;
any unexpected and/or uncontrolled eye movements such as nystagmus or divergent or
unilateral strabismus

Should any of the vision assessments (Snellen visual acuity, confrontational visual test field, or ocular motility) suddenly worsen after the injection of the filler, the treating investigator must examine the subject to exclude vascular injection and contact an eye specialist if necessary.

In addition, any one of the following changes in visual examinations after Baseline will be considered abnormal and clinically significant:

- Snellen acuity test: any change of 1 line or more
- Confrontational visual field test: change to the peripheral vision
- Ocular motility: change to ocular motility

If any of the above changes occur at any assessment, the change should be reported as an AE and the subject must be referred to an ophthalmologist to evaluate if the resulting change is related to a vascular injection of the dermal filler. If the ophthalmologist confirms that the the result is related to a vascular injection of the dermal filler, the subject should be treated per standard of care for intravascular injection of dermal filler. The subject will be withdrawn from the study and the need for stopping the study will be reviewed.

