12.1 Definitions of Adverse Events and Adverse Device Effects

Adverse Event (AE)

An AE is defined as any untoward medical occurrence, unintended disease or injury or any untoward clinical signs in subjects, users or other persons. This definition includes events whether or not related to the IMDs and those events related to the procedures involved.

Adverse Device Effect (ADE)

An ADE is defined as an AE that is related to the use of the IMDs. This includes any AE resulting from insufficiencies or inadequacies in the IFU, the deployment, the implantation, the installation, the operation, or any malfunction of the IMDs. In addition, this includes any event that is a result of a use error or intentional misuse of the IMDs.

Those AEs occurring after provision of informed consent and prior to application of the IMDs will be recorded as part of the medical/aesthetic procedures history. Any medical condition that is present at the time that the subject is screened should be also considered as medical/aesthetic procedures history and not recorded as an AE (see Section 10.9). However, if the condition deteriorates at any time from date of administration of the IMDs during the clinical investigation, it should be recorded and reported as an AE.

For a list of anticipated AEs and anticipated ADEs please refer to Section 6.1. In addition, the following events could specify as Adverse Events of Special Interest (AESI);

- Changes in vision (i.e. loss of vision, blurriness, double vision, pain in or around your eye, blindness, blind spots, problems moving the eyes, change in peripheral vision)
- Skin changing color around the eyelids or around the site of injection

Serious Adverse Event (SAE)

An SAE is defined as an AE meeting one or more of the following conditions:

- led to death
- led to serious deterioration in health of the subject that either resulted in:
 - o a life-threatening illness or injury, or

- o a permanent impairment of a body structure or a body function, or
- o in subject hospitalization or prolonged hospitalization, or
- o medical or surgical intervention to prevent life-threatening illness or injury or permanent impairment to a body structure or a body function
- led to fetal distress, fetal death, or a congenital abnormality or birth defect
- is an important medical event

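### Study-wide suspension after a vascular occlusion depends on the event being unanticipated, and the protocol gives opposite answers on whether an occlusion after correct technique is

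*Protocol*

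**What the plan says.** The stopping rule is in protocol Section 12.4.1, and Section 18 refers to it for vascular occlusion. Its scope is wide: "this encompasses vascular embolic events which may lead to skin necrosis, vision loss or stroke".

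- **Every occlusion:** "In the event that such a complication occurs, the enrollment and treatment at the investigational site will be suspended and a root cause investigation" must follow.
- **Technique not correct:** "If the investigator didn't properly follow the treatment procedure, he/she will be re-trained before being allowed to recruit further subjects".
- **Technique correct:** "In case this event was unanticipated and the investigator did follow the treatment procedure correctly, the entire clinical investigation has to be immediately suspended". Enrollment then waits until the event is characterized and a strategy to avoid it is devised.

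The unanticipated device effect definition in the same section applies "if that effect, problem, or death was not previously identified in nature, severity, or degree of incidence in the investigational plan or application", and adds a residual limb for other unanticipated serious problems.

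Three other places bear on the word *unanticipated* or on the same events:

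- Section 12.1: "For a list of anticipated AEs and anticipated ADEs please refer to Section 6.1".
- Section 6.1: "Rare but serious adverse events associated with the unintended intravascular injection of dermal fillers in the face have been reported". It goes on to name vision impairment, blindness, stroke and skin necrosis.
- Section 6.3 says that, with correct injection by a trained and experienced user, serious device effects are not expected.

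For visual changes that an ophthalmologist confirms as related to vascular injection, Section 10.8.4 says: "The subject will be withdrawn from the study and the need for stopping the study will be reviewed". The synopsis has the same consequence.

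**The concern.** The mandatory study-wide step has two joint conditions, and the first is a classification that the protocol does not settle for the events in question. Sections 12.1 and 6.1 put these outcomes on the anticipated list. Section 6.3 suggests that the same event after correct technique would not be expected. A site, the sponsor and an IRB could each read the protocol carefully and differ on whether the whole investigation must be suspended at once.

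The events are blindness, stroke and tissue necrosis in an aesthetic trial, and the decision has to be made quickly. If the 12.1/6.1 reading prevails, other sites could continue injecting, including repeat-treatment with the investigational filler in both folds, while the affected site is under root cause investigation.

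**Working it through.** No arithmetic applies. The check follows the rule's two conditions through the text.

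**Step 1: are the covered outcomes on the anticipated list?** Section 12.4.1 covers embolic events that may lead to skin necrosis, vision loss or stroke. Section 6.1, which 12.1 cites as the list, names all three. In *nature*, then, they are identified in the plan.

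**Step 2: can *unanticipated* be met another way?** The definition in 12.4.1 also counts severity and degree of incidence.

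- Severity: 6.1 already includes permanent vision impairment, blindness and stroke, so little room is left.
- Incidence: the visible text offers only the word rare. Some of the material around Sections 6.2 and 6.3 is not visible, so the lack of a figure is not counted as an omission.
- The residual limb itself uses the word unanticipated, so it does not settle the classification.

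**Step 3: what follows in each of the 2 × 2 = 4 combinations?**

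| Event classed as | Procedure not followed | Procedure followed |
|---|---|---|
| Unanticipated | Site suspended, root cause, retraining | Site suspended, root cause, whole investigation suspended |
| Anticipated | Site suspended, root cause, retraining | Site suspended, root cause, **no further step or restart condition in 12.4.1** |

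Three combinations are resolved and one is not. On the 12.1/6.1 reading, an occlusion after correct technique falls in the unresolved one. On the 6.3 reading it falls in the cell above, with immediate study-wide suspension.

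**Step 4: does another section fill the open cell?** Section 10.8.4 does so in part. A vision change confirmed as related to vascular injection leads to a review of the need to stop, regardless of anticipation or technique. It names no reviewer, no time limit and no interim status for the other sites. It does not reach necrosis or stroke without a vision change.

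**Step 5: what do the restart terms cover?** Site suspension covers enrollment and treatment, so touch-up and repeat injections stop there. The terms for resuming refer only to recruiting or enrolling. The synopsis plans about 20 weeks of recruitment from a start in Q1 to Q2 2019, while the current version is dated March 2021 and adds Visit 7c for repeat-treatment. Assuming recruitment ran to plan, the injections still to come are repeat-treatments, which those terms do not mention.

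**Step 6: does the SAP settle the word?** No. SAP Section 9.3 judges an unanticipated serious device effect against the Investigator's Brochure and an anticipated one against the risk analysis report. The protocol uses the investigational plan or application.

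**The case against.** The strongest defense is Section 6.3. It addresses the disputed case, a serious event after correct injection, and supports calling such an event unanticipated, so that the study-wide branch fires. Section 6.1 lists what has been reported for fillers in general and does not separate correct from incorrect technique. This stands as a reason not to say that the branch can never be met. It does not remove the difficulty: 12.1 still designates 6.1 as the anticipated list, and if every occlusion after correct technique were unanticipated, the first condition would add nothing to the second. The study-wide branch does call the occlusion unanticipated when it describes resumption, but only after making that a condition.

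A reader might infer that an occlusion after correct technique triggers no study-level action at all. The documents do not support this. Section 10.8.4 and the synopsis require a stopping review for vision changes related to vascular injection, every occlusion suspends the affected site, and serious events are reported within 24 hours. Under Section 18 the sponsor may terminate for any reason, and a principal investigator, IRB or FDA may suspend or terminate at the sites for which they are responsible. These are real safeguards, but apart from the 10.8.4 review they do not oblige anyone to take a study-level step.

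A reader might also infer that several occlusions at different sites could not meet the trigger. That is not shown, because a cluster could be judged beyond rare and so unanticipated in degree of incidence. Nor do the documents say that the device is the likeliest cause when technique was correct; the root cause investigation exists to find that out.

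Finally, the application and the device safety management plan are not available here and may say more.

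**Conclusion.** The concern holds as an internal contradiction in a safety rule. Sections 12.1 and 6.1 on one side, and 6.3 on the other, give opposite answers on whether an occlusion after correct technique requires immediate suspension of the whole investigation. On the first reading the mandatory suspension would normally not fire for the events it was written for, and one of four branches in 12.4.1 has no stated next step.

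The gap differs by event. For vision changes related to vascular injection, the review under 10.8.4 remains. For necrosis or stroke without a vision change, the visible text has no mandatory study-level step.

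This should be resolved before further injections are given, because following the rule as written can defeat its purpose. The conclusion rests on the visible text and on reading Section 6.1 as the anticipated list, as 12.1 directs. It does not rest on any event rate.

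**What to change.** Reconcile protocol Sections 6.1, 6.3, 10.8.4, 12.1 and 12.4.1, the synopsis, and the definition in SAP Section 9.3, so that the text states:

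1. whether an occlusion after correct technique counts as unanticipated for this rule, and against which reference document;
2. what follows, including the condition for restarting the site, when the event is anticipated and the procedure was followed;
3. whether the restart terms cover touch-up and repeat injections as well as enrollment;
4. how the review in 10.8.4 relates to the suspension in 12.4.1.

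The sponsor and its safety reviewers must choose the rule; none is proposed here. The cost is a wording amendment to the protocol, a matching SAP edit and notice to the sites, with no new data or procedures. The downside is a possible pause of the trial that one reading of the current text would not require.

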12.5 Adverse Events/Serious Adverse Events Follow-up

The investigator will take all appropriate and necessary measures required for resolution of the AE. Should this include prohibited medication, the investigator will contact the Medical Monitor in order to seek advice.

All AEs must be followed-up by the investigator until recovery, or until the investigator determines that the subject's condition is stable, or until the last day of the clinical investigation at the site, whichever occurs first.

Any pregnancy must be followed-up until the pregnancy outcome on the pregnancy report form. If it is still on-going at the end of the clinical investigation, follow-up will be continued outside of the context of clinical investigation and pregnancy outcome (including pregnancy duration

and health status of a newborn or cause of premature termination, as applicable) will be reported to the Sponsor.

All SAEs judged to be related to the IMDs (SADEs) must be followed by the investigator until the subject has recovered, recovered with sequelae, died, or until the investigator determines that the subject's condition is stable, whichever occurs first. In case the clinical investigation ends before an SAE is resolved, the last status should be recorded. Every possibly effort should be made in order to follow up on SAEs until their resolution.

12.6 Visual Examinations

For details of visual examinations, see Section 10.8.

12.7 Device Deficiencies

12.7.1 Definition of a Device Deficiency

A device deficiency is defined as an inadequacy of an IMD with respect to its identity, quality, durability, reliability, safety or effectiveness. Deficiencies include malfunctions, use errors and inadequate labeling.

12.7.2 Recording and Reporting of Device Deficiencies

Device deficiencies should be reported to the Safety Department of will forward the deficiency report to the sponsor within 24 hours after receipt of the respective report from the treating investigator.

Device deficiencies will be recorded as per relevant SOPs from the CRO. In case a device deficiency is associated with an AE, additionally, the corresponding AE documentation procedures must be adhered to (see Section 12.2).

12.7.3 Handling of Deficient Medical Devices

Any medical device alleged to be deficient must not be used by the treating investigator and must be returned to Croma-Pharma GmbH or its representative or destroyed according to the site's procedures, after device accountability has been performed.

Assessment of Effectiveness

Effectiveness will be determined using a well defined, valid and reliable scale, the NLF-SRS (outlined in Section 10.1). The scale and the proposed instructions for its use by treating investigators is outlined in the manual.

Response is defined as having at least one grade improvement over Baseline on the 5-point NLF-SRS.

Scores are assessed as 1 (None/minimal), 2 (Mild), 3 (Moderate), 4 (Severe), 5 (Extreme).

14

Statistical Considerations

The statistical analyses will be described in detail in a statistical analysis plan.

14.1 Analysis Sets

The statistical analyses will be based on the following data sets:

Full Analysis Set (FAS)

The Full Analysis Set (FAS) consists of all randomized subjects who received at least one administration of Princess[®] FILLER Lidocaine and the control medical device at the same visit; subjects who receive only one treatment (only Princess[®] FILLER Lidocaine or only Juvéderm[®] Ultra XC) during initial treatment will be excluded from the FAS. The analyses based on the FAS will use the randomized treatment groups.

Per-Protocol Analysis Set (PPS)

The Per-Protocol Set (PPS) is defined as a subset of the subjects in the FAS who had no major protocol deviations. A possible per protocol analysis population bias will not be influenced by the exclusion criteria due to the split face design. The excluded subjects due to protocol deviations will be discussed in detail while the statistical analysis plan is being prepared and definitively ahead of the database lock in order to identify any possibly bias.

Safety Analysis Set (SAF)

The Safety Analysis Set (SAF) comprises all subjects who were randomized and received at least one treatment (i.e., any dose of Princess® FILLER Lidocaine or the control medical device). The analyses based on the SAF will use the actual treatment groups.

14.2 Statistical Analyses

The PPS and the FAS will be both considered equally important for the primary analysis; the primary analysis will be performed with the FAS; if Princess® FILLER Lidocaine can be considered non-inferior to Juvéderm® Ultra XC according to this analysis, the sensitivity analysis based on the PPS can be considered confirmatory. Otherwise, this analysis has to be considered exploratory. Non-inferiority is demonstrated only if the results are consistent for both analysis data sets.

Page 105 of 133

15 Mar 2021

All effectiveness analyses will be conducted for the FAS and subsequently for the PPS . Safety analyses will be based on the SAF.

Effectiveness

The primary effectiveness outcome measure will be evaluated by means of a one-sided 95% confidence interval for the difference in paired proportions p_A - p_B . At this, p_A is the response rate for Princess® FILLER Lidocaine and p_B is the response rate for Juvederm® Ultra XC. Thus, a negative value for this difference means that the response rate of Princess® FILLER Lidocaine is lower than the response rate for Juvederm® Ultra XC. Princess® FILLER Lidocaine will be considered non-inferior to Juvederm® Ultra XC if the lower confidence limit exceeds the non-inferiority margin of -10% and thus if the null hypothesis H0: p_A - p_B \leq -10% can be rejected. In addition to this, the response rates for both treatment groups will be tabulated.

In order to assess the homogeneity of the primary effectiveness outcome measure and of the treatment effect among the clinical investigational sites, a mixed logistic regression model with treatment, site, and treatment-by-site interaction as fixed effects and random subject effects will be fitted. Small clinical investigational sites with less than ten subjects will be pooled and a two-sided alpha level of 15% will be used to test for a treatment-by-site interaction. In case that the treatment-by-site interaction is not statistically significant (at the alpha level mentioned above), the treatment-by-site interaction will be removed from the mixed model and the confidence interval for the difference in proportions will be derived from this mixed model adjusted for site effects. If the treatment-by-site interaction effect is statistically significant (at the alpha level mentioned above), the treatment difference is not interpretable in the model. In this case, the treatment difference in the main effect model without adding the interaction effect is tested and in addition, the treatment difference by site will be presented and observed heterogeneities will be evaluated.

Subjects with missing NLF-SRS grades at Baseline and/or at Week 24 will be considered as non-responders for the primary analysis. Since it is very unlikely that the assessment of only one NLF will be missing, presumably either no or both assessments will be available for one subject at a certain time point. Therefore, this imputation method will probably decrease the response rate in both treatment groups simultaneously. Due to the fact that the sample size calculation was based on rather high response rates (88% for Juvederm® Ultra XC and 87% for Princess® FILLER Lidocaine), lower response rates will make it more difficult to demonstrate

non-inferiority of Princess® FILLER Lidocaine and thus this approach is considered to be conservative. In addition to this approach, a complete case analysis (using the available data without any imputation), a best-case analysis (missing values for Princess® FILLER Lidocaine will be considered as a response, missing values for Juvéderm® Ultra XC will be considered as a non-response), a worst-case analysis (missing values for Princess® FILLER Lidocaine will be considered as a non-response, missing values for Juvéderm® Ultra XC will be considered as a response), and a tipping point analysis will be conducted as sensitivity analyses.

The statistical analysis of the secondary and additional outcome measures will be described in detail in the statistical analysis plan. A hierarchical testing procedure will be applied for the analysis of the primary outcome measure, as well as the secondary outcome measures 1 and 2, in order to control multiplicity. At this, the following order will be used:

- 1. Analysis of primary outcome measure based on FAS
- 2. Analysis of primary outcome measure based on PPS
- 3. Analysis of secondary outcome measure 1 based on FAS
- 4. Analysis of secondary outcome measure 1 based on PPS
- 5. Analysis of secondary outcome measure 2 based on FAS
- 6. Analysis of secondary outcome measure 2 based on PPS

For qualitative variables the frequencies (absolute and relative) will be calculated and compared between the treatment groups. Quantitative parameters will be described by declaring the mean value, standard deviation, minimum, first quartile, median, third quartile, and maximum per treatment group. In addition to this, mean value (incl. two-sided 95% confidence interval), standard deviation, minimum, first quartile, median, third quartile, and maximum will also be provided for the difference in quantitative parameters between the two treatment sides of a subject. The secondary outcome measures 1 and 2 will be analyzed as described for the primary effectiveness outcome measure. Descriptive statistics will be used to summarize the remaining outcome measures. Kappa statistics will be calculated in order to assess inter-rater consistency among the three independent blinded photographic reviewers.

Safety

Safety variables will be analyzed based on the SAF. Adverse events will be coded by the MedDRA. Incidence of AEs will be summarised by preferred term (PT) and system organ class

15 Mar 2021

(SOC). AEs (SOC and PTs) will be summarised also by intensity, relationship to the IMDs or procedure and seriousness. All AEs will be properly listed (by subject, type, date, treatment and time since last treatment [first injection or touch-up]).

